Additional GLMs for binary and count outcomes and analysis of covariance models for continuous outcomes, as appropriate for each outcome above, will analyze the effects of covariates and their interactions with the treatment effect.

Aim 4 (Family-level outcomes): The P-CPQ, FIS, and satisfaction and acceptability scores will be compared between the SDF and placebo-treated groups using analysis of covariance, with trial site included as a covariate.

Additional analyses will consider the effects of covariates and their interactions with the treatment effect.

Changes in the color of treated lesions over time will be compared between treatments using a Cochran-Mantel-Haenszel chi-square test, with trial sites as the strata.

The family's experiences with ECC, child's brushing and dietary habits, and color change will be examined as additional covariates for the analyses of satisfaction and acceptability scores.

Safety: The proportion of infected trial teeth at each visit will be compared between the SDF and placebo-treated groups using a generalized estimating equation (GEE) model for binary outcomes, using an exchangeable correlation to account for possible non-independence among multiple teeth within a participant. Trial site will be included as a covariate.

The proportion of participants with adverse events (gum infection, oral mucositis, allergic reaction, anaphylaxis, nausea, vomiting, gastrointestinal pain, diarrhea; individually and the presence of any of the events) during the follow-up period will be compared between the SDF and placebo-treated groups using Cochran-Mantel-Haenszel chi-square tests, with trial sites as the strata.

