Note: This global transition judgment question will be included at follow-up visits for assessing the responsiveness of the OHRQoL measures in children with ECC (Locker et al., 2004). If the use of SDF had improved the participants’ lives, we would expect to see a substantial fall in P-CPQ scores between baseline and follow-up in the children who had received the SDF. This will be determined using the effect size, a unitless measure of change in mean score which is calculated by subtracting the follow-up score from the baseline score and dividing the result by the standard deviation of the mean baseline score for that group. This global transition judgment (which is a single question which basically asks them to judge whether they got better, got worse or stayed the same) serves both as a concurrent validity check for the change in P-CPQ score (in the same way that the global item earlier serves as a concurrent validity check at baseline, as described above) and also as an outcome measure in its own right.

2. P-CPQ 16-item version

The following questions ask about symptoms and discomfort that children may experience due to the condition of their teeth, lips, mouth and jaws.

During the last 3 months, how often has **YOUR CHILD**:

Had pain in the teeth, lips, jaw or mouth?

Never	Once or twice	Sometimes	Often	Every day or almost every day	Don't know
-------	---------------	-----------	-------	-------------------------------	------------

Had food stuck in the roof of the mouth?

Never	Once or twice	Sometimes	Often	Every day or almost every day	Don't know
-------	---------------	-----------	-------	-------------------------------	------------

Had bad breath?

Never	Once or twice	Sometimes	Often	Every day or almost every day	Don't know
-------	---------------	-----------	-------	-------------------------------	------------

Had food caught in or between the teeth?

Never	Once or twice	Sometimes	Often	Every day or almost every day	Don't know
-------	---------------	-----------	-------	-------------------------------	------------

Had difficulty biting or chewing firm foods such as fresh apple, corn on the cob or firm meat?

Never	Once or twice	Sometimes	Often	Every day or almost every day	Don't know
-------	---------------	-----------	-------	-------------------------------	------------

Had trouble sleeping?

Never	Once or twice	Sometimes	Often	Every day or almost every day	Don't know

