3. TRIAL OBJECTIVES AND OUTCOME MEASURES

The trial objectives are as follows:

- Aim 1: The primary aim of this trial is to assess the efficacy of 38% SDF applied once, to arrest cavitated lesions (caries lesions with cavities that expose dentin clinically, but with no pulp exposure, pain, mobility, or clinical signs of pulpal infection) in the primary dentition (assessed using the International Caries Detection and Assessment System-ICDAS II activity criteria, Appendix A) at 6-month follow-up.
- Aim 2: The first secondary aim is to assess the efficacy of 38% SDF applied twice, approximately 6 months apart, to arrest cavitated lesions in the primary dentition at approximately 8 months after initial application. A comparison of the effect of one application will be assessed over time at 3- and 6-month follow-ups (Sub-Aim 2a).
- Aim 3: The next secondary aim is to assess the impact of 38% SDF applied twice, approximately 6 months apart, on pain in children through use of the Dental Discomfort Questionnaire. The impact of 38% SDF on pain after a single application will be assessed at approximately 3 and 6 months (Sub-Aim 3a).
- Aim 4: The tertiary aim is to assess the effect of 38% SDF applied once (assessed at approximately 6 months after initial application) and twice, approximately 6 months apart (assessed at approximately 8 months after initial application), on family-level outcomes, assessing the impact on oral health-related quality of life (Sub-Aim 4a), and on treatment satisfaction and acceptability (e.g., associated with the change in color of treated lesions, etc.; Sub-Aim 4b). The relationship between treatment satisfaction/acceptability and other factors (e.g., family experience with ECC, oral hygiene and dietary habits) will be evaluated.

Additionally, safety will be assessed.

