3.3. Tertiary Outcome Measures

The following tertiary outcomes associated with the effect of 38% SDF on the Family will be assessed:

- Oral Health-Related Quality of Life (OHRQoL): OHRQoL will be assessed at baseline, 3-, 6-, and 8-month visits. Parents/legal guardians will be asked to complete the 16-item Parental-Caregiver Perception Questionnaire (P-CPQ) and 8-item Family Impact Scale (FIS) questionnaire (See Protocol Appendix C). The P-CPQ and FIS total and subscale scores are computed by summing the scores.
- Treatment Satisfaction and Acceptability: This will be assessed at baseline/24-48 hour contact/visit, and 3-, 6-, and 8-month visits using the questionnaire labeled as Family Survey (See Protocol Appendix D). Parents/legal guardians in each treatment arm will be asked about their level of satisfaction with the appearance of their children's teeth, and their overall level of acceptance and satisfaction with the treatment received. They will also be asked about their family experiences with ECC, as well as the child's brushing and dietary habits, and these items will be correlated with acceptability and satisfaction (e.g., adults having prior experience with the consequences of ECC and associated stress might be more accepting of this treatment alternative). In addition, color of treated lesions will be determined (yellow, brown, black), not as a primary indicator of lesion activity, but the change in color over time will be used for both trial arms as a measure of consequences associated with treatment assessed in the satisfaction questionnaire.

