6.7. Demographic and Baseline Characteristics

The comparability of treatment groups with respect to participant demographics and baseline characteristics will be assessed in a descriptive manner, but no formal statistical testing will be performed. Standard continuous or categorical variable summaries will be presented by treatment group for demographic and baseline characteristics in each of the analysis populations.

Standard descriptive statistics will be presented for the demographic continuous variables, e.g.:

- Number of Children Living with You
- Number of Adults Living with You

Total counts and percentages of participants will be presented for the demographic categorical variables including:

- Age (1, 2, 3, 4, 5 years)
- Sex
- Race
- Ethnicity
- Primarily non-English spoken at home
- Study site
- Is a Household Adult Employed
- Number of Children Living with You
- Number of Adults Living with You
- Household Income

Standard descriptive statistics will be presented for the baseline characteristic continuous variables:

- Number of study teeth per subject
- Number of study lesions per subject
- dmfs (number of decayed, missing, and filled surfaces)
- dmft (number of decayed, missing, and filled teeth)
- P-CPQ FL
- P-CPQ EW
- P-CPQ SW
- FIS
- FIS PE

- FIS PF
- FIS FC
- Child's Teeth and Mouth Health
- How much is Child's Overall well-being affected by the condition of his/her teeth, lips, jaw or mouth
- How Much is Family's Daily Life Affected your child's teeth lips, jaws or mouth

Total counts and percentages of participants will be presented for the baseline characteristic categorical variables of:

- Entry criteria met
 - Age <3 S-ECC: Any Caries
 - Age 3-5 S-ECC: upper anterior dmfs \geq 1
 - Age 3 S-ECC: dmfs \geq 4
 - Age 4 S-ECC: dmfs \geq 5
 - Age 5 S-ECC: dmfs $>$ 5
- Number of study teeth per subject
- Number of study lesions per subject
- Lesion location
 - Tooth
 - Anterior / Posterior
 - Maxillary / Mandibular
 - Surface
- ICDAS severity score for enrolled lesions
- Maximum ICDAS severity score for subject
- Frequency Child's Teeth are Brushed
- Who Brushes Child's Teeth
- Child Uses Fluoride Toothpaste
- Child Uses Prescription High-Fluoride Toothpaste
- Fluoride Painted/Put on Child's Teeth
- How Often Does Child Get Sugary Drinks
- How Often Does Child Get Sugary Snacks
- How Often Does Child Drink Water
- Parent's Satisfaction in Appearance of Child's Teeth
- Child's Satisfaction in Appearance of Child's Teeth

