6.11. Efficacy Analyses

All efficacy endpoints will be analyzed using the ITT and ITT2 populations. Additional analyses will be performed on the PP and PP2 populations.

The null hypothesis is no difference between the treatment groups and the alternative hypothesis is there is a difference between treatment groups. All statistical comparisons will be made using a two-sided test. The interim and final analyses will be conducted using p-value thresholds of 0.000001709 and 0.00099938, respectively. The overall type I error for interim and final primary endpoint analysis is two-sided $\alpha=0.1\%$.

Several categorical variables that are to be used as covariates in the GEE model will have categories collapsed due to small sample sizes. Race and ethnicity will be combined to form a single combined variable defined as: Hispanic or Latino if a subject indicated as such for ethnicity, multiracial if more than one race was selected, Black, White, “Asian or ‘American Indian or Alaska Native’ or ‘Native Hawaiian / Other Pacific Islander’”, “Not Reported” or Unknown”. Within the ‘tooth’ variable, lower incisors (LL1, LL2, LR1, LR2) will be combined into a single category and LR6 will be combined with LR5 for the imputation models for the lesion arrest outcomes, and combined into upper jaw / lower jaw and anterior teeth (upper and lower central incisors, lateral incisors, and canines) / posterior teeth (upper and lower molars on the) variables for the imputation models for the presence of tooth pain outcomes. For the imputation models for the presence of tooth pain outcomes, child ages 1 and 2 years will be combined.

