6.11.5. Tertiary Efficacy Hypotheses, Endpoints, and Analyses

The P-CPQ (Sub-Aim 4a), FIS (Sub-Aim 4a), and satisfaction and acceptability scores (Sub-Aim 4b) will be compared between the SDF and placebo-treated groups using analysis of covariance (ANCOVA). The models will include study site as a covariate due to stratified randomization by site. Additional ANCOVA models will consider the effects of covariates and their interactions with the treatment effect.

Changes in the color of treated lesions over time will be summarized by group.

The family's experiences with ECC, child's brushing and dietary habits, and color change will be examined as additional covariates for the analyses of satisfaction and acceptability scores.

The total number of episodes of pain associated with trial teeth per participant (calculated by adding all reports of pain throughout the trial verified by a clinical exam to be associated with a trial tooth) during the follow-up period and the DDQ scores will be summarized for the SDF and placebo treated groups. Due to the small number of participants with any pain, no statistical comparisons will be performed for the number of episodes of pain or the DDQ scores.

Additional analyses of the proportion of arrested lesions at 3-months, 6-months, and 8-months will extend the GEE models for binary outcomes to include covariates and their interactions with the treatment effect; covariates will include race/ethnicity, gender, age, trial site, initial ICDAS score, tooth location (anterior/posterior; as there are some data in the literature to suggest a difference in SDF efficacy) and number of affected teeth. Interactions of the covariates with treatment will be explored to examine the results for differential treatment effects. However, the analyses are not specifically powered to detect these interactions. Due to the small number of participants with any pain, no analyses which include covariate effects on the binary pain outcomes will be performed.

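### The main between-arm ANCOVA of P-CPQ and FIS names study site as its only covariate and leaves out the baseline value of the same score, which the trial collects; precision is lost on tertiary endpoints.

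*SAP*

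**What the plan says.** SAP 6.11.5 compares P-CPQ, FIS, satisfaction and acceptability scores between arms by ANCOVA and adds: "The models will include study site as a covariate due to stratified randomization by site". Protocol 12.4 (Aim 4) has the same model, "using analysis of covariance, with trial site included as a covariate". No other covariate is named for the main comparison of P-CPQ and FIS.

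The surrounding text bears on the point as follows.

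- **Visits.** SAP section 3 sets Aim 4 as the effect of SDF "applied once (assessed at approximately 6 months after initial application) and twice, approximately 6 months apart (assessed at approximately 8 months after initial application".
- **Baseline data.** SAP 3.3 states that "OHRQoL will be assessed at baseline, 3-, 6-, and 8-month visits". SAP 6.7 lists the three P-CPQ subscales, the FIS and its three subscales among the items covered by "Standard descriptive statistics will be presented for the baseline characteristic continuous variables".
- **Further models.** SAP 6.11.5 continues: "Additional ANCOVA models will consider the effects of covariates and their interactions with the treatment effect". It lists no covariates for P-CPQ or FIS. The same section does list them for lesion arrest and for satisfaction and acceptability.
- **Analysis sets.** SAP 6.11 says "All efficacy endpoints will be analyzed using the ITT and ITT2 populations", with additional analyses on PP and PP2.
- **Imputation.** SAP 6.11 imputes family outcomes by predictive mean matching, and results at prior visits are among the predictors.
- **Benefit as the protocol describes it.** Appendix C says that, if SDF helped, "we would expect to see a substantial fall in P-CPQ scores between baseline and follow-up in the children who had received the SDF". It measures this by a within-group effect size.

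**The concern.** A questionnaire score measured before treatment is usually the best single predictor of the same score afterwards. Leaving it out of the between-arm model puts variation that could be explained into the residual, so the confidence interval for the treatment difference is wider than it needs to be. The trial has already paid for the baseline measurement.

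Three places might have put baseline into the model, and none does. The imputation model uses it to fill in missing follow-up scores, but that is separate from the analysis model. The additional ANCOVA models name no covariates for these scales. The Appendix C effect size is computed within one group and does not compare the arms.

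At stake is the precision of Sub-Aim 4a. The primary endpoint and the two key secondary endpoints are not touched.

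**Working it through.** **Plan's own figure.** There is none to reproduce. The documents give no SD, target difference, power or correlation for P-CPQ or FIS. The 1144 in SAP section 4 is sized on lesion arrest and serves here only to set the scale, at 1144/2 = 572 per arm.

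**Inputs.** Allocation is 1:1, stratified by site (SAP section 5). Attrition is 10% (Protocol 12.2). Assumptions: equal SD at baseline and follow-up, and r between 0.2 and 0.7.

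**Relative variance of the treatment difference, complete data**

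- follow-up score, site only: 1
- change from baseline, site only: 2(1 − r)
- baseline as covariate, either response: 1 − r²

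So adding baseline multiplies the standard error by √(1 − r²) if the response is the follow-up score. If it is change, the factor is √[(1 − r²)/(2(1 − r))] = √[(1 + r)/2].

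| r (assumed) | Ratio, follow-up score | SE smaller by | Ratio, change | SE smaller by |
|---|---|---|---|---|
| 0.2 | √0.96 = 0.980 | 2% | √0.60 = 0.775 | 23% |
| 0.3 | √0.91 = 0.954 | 5% | √0.65 = 0.806 | 19% |
| 0.5 | √0.75 = 0.866 | 13% | √0.75 = 0.866 | 13% |
| 0.7 | √0.51 = 0.714 | 29% | √0.85 = 0.922 | 8% |

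In SD units at 572 per arm, the site-only follow-up comparison has a standard error of √(2/572) = 0.059. With baseline it is 0.056, 0.051 and 0.042 for r = 0.3, 0.5 and 0.7.

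**Visit value or change.** Take a chance baseline imbalance of one standard error (0.059 SD). It moves the site-only follow-up estimate by r × 0.059 = +0.018, +0.030 and +0.041 SD for r = 0.3, 0.5 and 0.7. It moves the site-only change estimate by (r − 1) × 0.059 = −0.041, −0.030 and −0.018 SD. Once baseline is a covariate, the choice no longer matters: subtracting baseline from the response only lowers the baseline coefficient by 1, and the treatment estimate and its standard error are the same.

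**Missing data.** This was simulated for the follow-up score: N = 1144, three sites, no treatment effect, follow-up missing at random, 25 imputations by predictive mean matching, Rubin's rules, 300 trials per setting. Imputation used baseline and site only. That simplifies the SAP 6.11 model, which also uses race/ethnicity, gender, age, maximum ICDAS score, an arrest indicator and other prior visits. Ratios of pooled standard errors, with baseline against site only:

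| Setting | r = 0.2 | 0.3 | 0.5 | 0.7 |
|---|---|---|---|---|
| 10% missing | 0.982 | 0.958 | 0.876 | 0.731 |
| 20% missing | 0.983 | 0.961 | 0.887 | 0.744 |
| 10% missing, half the scores at zero | 0.989 | 0.974 | 0.916 | 0.794 |

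In the last row the observed correlations fall to about 0.16, 0.24, 0.43 and 0.63.

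**Where r is likely to lie.** Protocol 5.2 excludes children with a DDQ score of 1 or more at baseline, and Appendix C scores a response of Don't know as 0. Both push baseline scores towards zero, which makes the lower part of the range plausible.

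**The case against.** The strongest case against is that this is only a preference for efficiency. The outcomes are tertiary, lie outside the gatekeeping hierarchy of SAP 6.11.4, and are described in Protocol 3.2.3 as not meant for labeling. If one assumes a two-sided 5% level, which the documents do not set for these scores, 80% power with complete data is reached at (1.960 + 0.842) × 0.0591 = 0.166 SD with site only. With baseline at r = 0.3 it is reached at 2.802 × 0.0564 = 0.158 SD. No decision turns on that difference. This stands as a limit on importance. It does not make the site-only model the better choice when the covariate is already in hand.

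It is also fair that the table shells are kept in a standalone document (SAP section 11) and that the additional ANCOVA models leave room for baseline. They might include it, but the SAP does not say so.

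A reader might infer more than the documents support:

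- *That the dependent variable is left undefined.* SAP 6.11.5 names the scores, SAP 3.3 defines them as summed totals and subscales, and Aim 4 gives 6 and 8 months. Where the section means change, as for lesion colour, it says so. Only the explicit choice of visit value over change is missing.
- *That the comparison is biased.* Randomization protects the site-only estimate on average.
- *That baseline is ruled out.* It is not named, which is a weaker statement.
- *That baseline was dropped late.* The protocol already had the site-only model.

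**Conclusion.** The point holds as a minor improvement. The main between-arm ANCOVA of P-CPQ and FIS names site and does not name the baseline value of the same score. The site-only result is valid, and no efficacy or safety conclusion is threatened.

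On the plain reading of the response, the loss is a standard error that could be about 2% to 29% smaller across r = 0.2 to 0.7. Roughly 1% to 5% is the more cautious expectation if r is 0.2 to 0.3. If change from baseline were meant, the gain would be about 23% falling to 8% over the same range. The size rests entirely on an assumed r and on equal SDs. The missing-data figures rest also on an imputation model simpler than the planned one. The finding that baseline is not named rests on the text alone.

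**What to change.** In SAP 6.11.5, state that the ANCOVA for each P-CPQ and FIS total and subscale score at 6 and 8 months includes treatment, site and the baseline value of that score. Say explicitly that the response is the score at the visit.

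In SAP 6.11, extend the imputation to missing baseline values. The paragraph is written for the 6- and 8-month analyses, and Protocol 2.3.1 lets caregivers decline any question. Leave Family Survey items 11–14 out of the change: Appendix D has them completed only after treatment, so they have no baseline.

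Record the change in SAP section 9 with its date, reason and masking status at that date, and keep the site-only model as a supporting analysis. This matters because the SAP already reflects accumulated data; for example, SAP 6.11.5 refers to the small number of participants with any pain. If unmasked results for these scores have already been seen, keep the site-only model as the prespecified result and label the adjusted model as added afterwards.

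The cost is one degree of freedom per model, no new data collection, and a second set of routine outputs. With eight scores (the seven listed in SAP 6.7 plus the P-CPQ total), two visits and four analysis sets, that is at most 8 × 2 × 4 = 64 further models.

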6.12. Safety Analysis

The safety analyses will be presented by the treatment received for the Safety Population.

6.12.1. Adverse Events

All reported AEs will be coded using the Medical Dictionary for Regulatory Activities (MedDRA) and summarized by System Organ Class (SOC) and Preferred Term (PT).

Analyses of AEs will be performed for those events that are considered treatment emergent AEs (TEAE), where treatment emergent is defined as: any AE with onset after the administration of study drug (SDF or placebo).

An overall summary of AEs without SOC and PT will be presented with the number and percentage of participants by treatment with any of the following types of AEs:

- TEAE
- TEAE by severity (mild, moderate, severe, life-threatening, fatal)

- TEAE by relationship to study drug (unrelated, related; where unrelated includes not related and unlikely related, and related includes possibly related, probably related, related)
- Serious TEAE
- TEAE leading to study drug discontinuation
- TEAE leading to death

In addition to the overall summary, the number and percentage of participants by treatment for each of the TEAE categories above will be summarized by SOC and PT. In these summaries, each participant will contribute only once to the incidence rate based on the most related occurrence and most severe occurrence of the AE. This is true regardless of the number of occurrences.

Summaries of TEAEs by SOC and PT will also include total number of unique AE occurrences, where unique AE occurrences include all events, regardless of whether the same participant experiences the same AE multiple times. However, if the end of a first occurrence and the start of a subsequent occurrence overlap, or the end of a first occurrence indicates “ongoing”, then this would be counted as only one occurrence.

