5.2 Participant Exclusion Criteria

An individual who meets any of the following criteria will be excluded from participation in this trial:

Child:

- Hereditary generalized developmental dental defects such as Amelogenesis Imperfecta and Dentinogenesis Imperfecta.
- Known allergy/sensitivity to silver or other heavy metal ions.
- Presence of any gingival or peri-oral ulceration, abscess or stomatitis.
- Participating in the foster care system at trial initiation.
- Toothache pain at baseline (based on Dental Discomfort Questionnaire score of 1 or higher (Appendix B)).
 - Note: If toothache pain occurs after baseline, the child remains eligible to continue in the trial as long as he/she has at least one trial tooth that meets tooth inclusion/exclusion criteria.
- Demonstrated inability to comply with trial protocol requirements (determination is at the Clinical Site Investigator’s discretion).
- Rickets.
- Osteopenia or osteoporosis (e.g., Osteogenesis Imperfecta, Ehlers-Danlos Syndrome, Marfan Syndrome, etc.).
- Chronic diseases such as chronic kidney disease, leukemia, lymphoma, rheumatic disorders, etc.
- Metabolic bone disease (e.g., Galactosemia, Glycogen Storage Disease Type 1, etc.).

- Chronic glucocorticoid, anticonvulsants, chemotherapy, bisphosphonate administration.
- Hypothyroidism, hyperparathyroidism, impaired glucose tolerance, hypocalcemia or hypophosphatemia.

Tooth:

- Pain due to caries at baseline (based on DDQ score of 1 or higher, Appendix B).
 - Note: If toothache pain occurs after baseline due to a trial tooth, the tooth is removed from the trial.
- Pulpal exposure, or signs of pulpal infection (abscess, fistula, swelling).
- Mobility not associated with expected exfoliation patterns.

Parent/Legal Guardian:

- Demonstrated inability to comply with trial protocol requirements (determination is at the Clinical Site Investigator's discretion).
- Inability to read and comprehend the consent document or trial questionnaires in the translated languages available.

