9 ASSESSMENT OF SAFETY

9.1 Specification of Safety Parameters

Parameters used to assess safety will include AEs spontaneously reported by the participant or observed by the investigator, solicited AEs captured by interviewing the child's parent or legal guardian, and events recorded from oral cavity examination. All AEs will be coded by system organ class and preferred term according to the terminology of the Medical Dictionary for Regulatory Activities (MedDRA®).

Monitoring of AEs will be conducted throughout the trial. All AEs, SAEs, and UPs will be captured any time after informed consent is obtained. In addition, all AEs will be captured until 7 days after the last day of trial participation. Serious adverse events (SAEs) will be captured until 30 days after trial participation. SAEs will be reported to the IND sponsor and to NIDCR within 24 hours of becoming aware of the event. Safety events will be reported to the sIRB according to their policies and guidelines. AEs will be followed until they are resolved, considered stable, the subject is lost to follow-up, or the AE is otherwise explained.

Cavitated caries lesions will have signs of progressing infection (e.g., abscess, fistula, etc.) recorded. Gingival tissue irritation (e.g., ulcerations and mucosal erythema, leukoplakia or darkening of pigmentation) will also be recorded. In addition we will record observed or reported: nausea, not eating, vomiting, difficulty swallowing or breathing, swelling around the lips or skin of the face, itchiness around the lips or skin of the face, hives or rash, stomach ache; or diarrhea.

Potential adverse reactions to the trial drug include

- Infection: Infection will be defined by changes in clinical signs (from examination) over time in each trial arm. The clinical criteria for the positive recording of infection are the clinical presence of swelling, dental abscess, or fistula. Assessments for infection are made at each clinical trial visit and unscheduled/emergency visit. (See Appendix E).
- Mucosal irritancy: children in each group experiencing gingival erythema, ulcerations, etc. will be recorded (See [Section 8.1.1](#) and Appendix E).
- Systemic effects/allergic reaction: children in each group reported or observed to have: nausea, not eating, vomiting, difficulty swallowing or breathing, swelling around the lips or skin of the face, itchiness around the lips or skin of the face, hives or rash, stomach ache, or diarrhea (See Appendix E).

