9.1.1 Adverse Events

An adverse event is any untoward or unfavorable medical occurrence in a human subject, including any abnormal sign (for example, abnormal physical exam or laboratory finding), symptom, or disease, temporally associated with the participant's participation in the research, whether or not considered related to the participant's participation in the research.

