Sample size for the 24-48 h post-treatment safety visit is justified based on the 95% upper bound for the difference in 'safety event' between SDF and control. Erythema and 'adverse event' rate in previous studies are around 10-15% in the controls. Thus, assuming no safety difference between the two groups, and events occurring in 15% of the participants, the study sample will produce an upper bound for the difference at most 4% above the observed difference. Sample size calculations were made using PASS 13.

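### The SAP defines treatment-emergent adverse events by onset alone, so an event recorded before the first application that keeps its onset date and then worsens is missing from every specified TEAE table

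*SAP*

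**What the plan says.** SAP 6.12.1 opens with two statements of different scope. The first covers everything: "All reported AEs will be coded using the Medical Dictionary for Regulatory Activities (MedDRA) and summarized by System Organ Class (SOC) and Preferred Term (PT". The second narrows it: "Analyses of AEs will be performed for those events that are considered treatment emergent AEs (TEAE". The definition that follows uses timing only: "treatment emergent is defined as: any AE with onset after the administration of study drug (SDF or placebo".

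Every table then specified in that section is a TEAE table: any event, severity, relationship, serious, leading to discontinuation and leading to death, and the same categories again by SOC and PT. For counting unique occurrences, two records become one "if the end of a first occurrence and the start of a subsequent occurrence overlap, or the end of a first occurrence indicates “ongoing".

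Protocol 9.1 starts recording at consent: "All AEs, SAEs, and UPs will be captured any time after informed consent is obtained". Protocol 9.1.1 defines an event broadly: "An adverse event is any untoward or unfavorable medical occurrence in a human subject, including any abnormal sign". It does not say whether worsening is a new event. Protocol 5.2 excludes "Presence of any gingival or peri-oral ulceration, abscess or stomatitis" at entry. Erythema, nausea, stomach ache and diarrhea are not named there.

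**The concern.** The protocol expects local irritation from SDF. Section 2.3.1 lists temporary soft-tissue irritation, including erythema, as a risk. Section 2.2 describes an earlier adult study in which erythema above grade 1 was transiently more frequent on SDF at 24 hours at one of two sites. That is an effect on grade. A definition based only on onset can miss an effect on grade in a child whose gums were already mildly inflamed.

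The omission can only lower the counted rate, and it lowers it more in whichever arm causes more worsening. SAP section 9 removes formal testing of adverse events, so the descriptive TEAE tables carry the comparison between arms. Protocol 12.4 planned to compare participants with events during follow-up and set no onset condition. SAP section 9 does not list the narrowing among its changes.

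**Working it through.** **Can such an event exist?**
- Adverse events are recorded from consent (Protocol 9.1), and the schedule in Protocol section 7 has an adverse-event assessment at baseline.
- Questionnaires may be completed after consent on a day other than the examination, and the soft-tissue exam comes before application (Protocol 7.2).
- Protocol Appendix E grades erythema (under oral mucositis), gastrointestinal pain, diarrhea and nausea as mild, moderate or severe, so worsening can be expressed in the adverse-event record.

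**Trace one record under each recording convention.** Take erythema noted as mild before application and moderate at the 24-48 hour visit.

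| How it is recorded | Counted as TEAE? |
|---|---|
| One adverse-event record, pre-application onset kept, severity updated | No; absent from every TEAE table |
| First record ongoing, second record opened with a later onset | The second meets the definition, but the overlap rule may merge it into the first; the SAP does not say which onset then applies |
| First record closed, new record opened | Yes |
| Baseline finding kept only as an exam finding, later adverse event opened | Yes |

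Neither document says which row applies.

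**Does the missing-date rule help?** SAP 6.3.6 assumes onset after study drug when a start date or time is missing and the status is unclear. That can bring in a baseline-day event with no clock time. It does not help when the finding was made at the pre-application exam, because its timing is then clear.

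**Size, on assumptions only.** The documents give neither the share of children with a recorded pre-application event (b) nor the share of those who worsen (w). With 1144 / 2 = 572 children per arm, the uncounted share of an arm is b × w and the number of children is 572 × b × w.

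| b | w = 5% | w = 10% | w = 15% |
|---|---|---|---|
| 5% | 0.25 points (1.4 children) | 0.5 (2.9) | 0.75 (4.3) |
| 10% | 0.5 (2.9) | 1.0 (5.7) | 1.5 (8.6) |
| 20% | 1.0 (5.7) | 2.0 (11.4) | 3.0 (17.2) |

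These are gross figures for one arm. The effect on the difference between arms is b × (w on SDF − w on placebo). For example, with b = 10% and worsening of 15% against 5%, it is 1.5 − 0.5 = 1.0 point. With equal worsening it is zero.

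**What the 4% in Protocol 12.2 is.** With a 15% event rate and 572 per arm, the standard error of the difference is √(2 × 0.15 × 0.85 / 572) = 0.0211. The one-sided 95% half-width is 1.645 × 0.0211 = 3.5 points, or 3.7 points with about 515 per arm after 10% attrition. The stated 4% agrees with this. It is the distance from the observed difference to its upper confidence bound, a measure of precision.

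**The case against.** A reader might infer that such an event disappears from every adverse-event summary. The documents do not support that. The first sentence of SAP 6.12.1 promises a summary of all reported events by SOC and PT with no TEAE limit, and SAP 6.3.3 lists all eCRF data. What stands is narrower: the event is absent from the TEAE tables. Listings give no rates by arm, and the all-events sentence specifies no comparison of severity.

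The stronger objection is that the loss depends on how worsening is recorded. The Manual of Procedures and case report forms may settle that, and they are not available here. Protocol 7.3.2 treats gingival irritation found at the 24-48 hour visit as an adverse event, and Protocol 9.3.1 says to record when in doubt, so a new record is plausible. This stands as a limit on the concern. It does not remove it, because the SAP definition should not rest on a convention that neither document states.

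Erythema is an inferred example. Neither document discusses worsening erythema. Appendix E files erythema under oral mucositis, so some examiners might treat visible erythema at entry as stomatitis and exclude the child. For gastrointestinal symptoms, only the interval from consent to application matters, and it can be a single visit.

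A reader might also set the 3-point upper figure beside the 4% in Protocol 12.2, or take this statement as a baseline prevalence: "Erythema and 'adverse event' rate in previous studies are around 10-15% in the controls". Neither use is sound. The first is a precision bound, not a tolerance for bias. The second is an event rate in controls in previous studies. A child who loses one event may also still count in the any-TEAE row through another.

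**Conclusion.** The definition has no worsening clause, and by its wording it drops from all specified TEAE tables an event that keeps a pre-application onset date and then worsens. That would hold even if the event became serious or led to stopping study drug, although expedited reporting under Protocol 9.4 would be unaffected.

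The size is unknown. On the assumed ranges it runs from a fraction of a point to about 3 points of an arm, before subtracting placebo worsening and only if worsening does not open a new record. No decision rule uses the TEAE rate, so the consequence is a possible understatement of local irritation in the descriptive safety tables. The change is worth making because it is specific and cheap and needs no new data collection.

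**What to change.** In SAP 6.12.1:

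1. Define a TEAE as *any AE with onset after the first administration of study drug, or present before it and increasing in severity after it*. Take the reference grade from the mild/moderate/severe grading in the adverse-event records. The soft-tissue exam uses a modified mucositis scale (Protocol 8.1.1), and neither document maps that scale to the adverse-event grades.
2. State that an increase in severity after application counts as treatment-emergent even where it overlaps an ongoing record.
3. Reconcile the sentence on all reported events with the TEAE-only sentence, by specifying an all-events table or by limiting the first sentence to coding.

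The cost is one clause, one programming condition and slightly higher event counts in both arms.
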